7 STATISTICAL ANALYSES

7.1 General Methods

7.1.1 Definitions

7.1.1.1 Baseline Value

Unless otherwise stated, for the short-term, and short-term and long-term analyses, for each subject, baseline value of a parameter (e.g., efficacy laboratory parameter, safety laboratory test, ECG, or physical measurement endpoint) is defined as the last assessment on or prior to the date of the first dose of the study medication.

7.1.1.2 Change and Percent Change from Baseline

Change from baseline to any Week t in short-term treatment period or short-term and long-term is defined as follows:

$$C_{\text{Week } t} = M_{\text{Week } t} - M_{\text{baseline}},$$

where:

$C_{\text{Week } t}$ is the change from baseline at Week t ,

$M_{\text{Week } t}$ is the measurement at Week t ,

M_{baseline} is the measurement at baseline.

Percent change from baseline to any Week t in short-term, or short-term and long-term, treatment period is defined as follows:

$$P_{\text{Week } t} = 100 \times (M_{\text{Week } t} - M_{\text{baseline}}) / M_{\text{baseline}}.$$

Where $P_{\text{Week } t}$ is the percent change from baseline at Week t , and $M_{\text{Week } t}$, and M_{baseline} are defined as above.

The “Week t ” to which a measurement belongs is determined using the conventions described in Section 8.2 and Section 8.4.

7.1.1.3 Handling of Missing Data

The main analysis for change from baseline specified for primary and secondary endpoints in following sections will use the repeated measures model.

Safety analyses include either subjects’ data “prior to rescue medication”, or “regardless of rescue medication”. For analyses based on “prior to rescue medication”, subjects’ data up to and on the date of the first dose of rescue medication, subject to the prescribed cut off of the IP treatment

discontinuation (see Section 0), will be used. For analyses based on “regardless of rescue medication”, subjects’ data are excluded only after treatment discontinuation based on the prescribed cut off days (see Section 0).

Efficacy tables are summarized for subjects “prior to rescue and treatment discontinuation” and “regardless of rescue and treatment discontinuation”. For analyses based on “prior to rescue and treatment discontinuation” subjects’ data will be included up to the earliest of the start of rescue medication, or last dose of study medication including the cuts off allowances described in Section 0. For analyses “regardless of rescue and treatment discontinuation” all subjects’ data will eligible for inclusion in the analyses.

This model assumes that the time course of the endpoint values for subjects who discontinue treatment or are rescued at a specified time point is consistent with the time course for subjects who are ongoing at that time point.

While utilizing models such as ANCOVA, for Hb1Ac analysis of change from baseline, the measurement closest to the target date is assigned as the Week 52 measurement and will be used. If no Week 52 measurement is available (subject has discontinued before Week 52, or measurement not taken at Week 52, though subject was not discontinued), then the last available earlier post-baseline measurement will be used (LOCF). For subjects who started rescue medication prior to Week 52, their last post-baseline measurement taken prior to or on the date of the first dose of rescue medication will be used in the “prior to rescue medication” analyses.

For safety analyses based on “regardless of rescue medication”, which exclude data after treatment discontinuation, all data will be eligible to be used until the prescribed cut off (see Section 0).

For urinary albumin to creatinine ratio (uACR) shift tables, if no week 52 data are available for a subject, then last available observation prior to week 52 is used.

Section 8 provides additional information regarding handling of missing or partial dates, inclusion of values, windowing, and values obtained post treatment.

The same methodology will be used in the ST+LT analyses at Week 156.

7.1.2 Longitudinal Repeated Measures Analysis

A longitudinal repeated measures analysis using “direct likelihood” will be performed. The SAS procedure PROC MIXED will be used. The preferred model will include the fixed categorical effects of treatment, week, and treatment-by-week interaction as well as the continuous fixed covariates of baseline measurement and baseline measurement-by-week interaction.

The following general model will be used:

$$C_{ijk} = \text{intercept} + \beta_1 [M_{\text{baseline},ij}] + \tau_i + \alpha_k + (\alpha \tau)_{ik} + (\alpha M_{\text{baseline}})_{ijk} + \text{error}_{ijk}$$

(Model 7.1.2.1)

where:

C_{ijk} is the change from baseline for subject j in treatment group i at time k ,

β_1 is the slope coefficient for the baseline measurement,

$M_{\text{baseline},ij}$ is the baseline measurement of subject j in treatment group i ,

τ_i is the mean effect of treatment group i ,

α_k is the mean effect at time k

$(\alpha \tau)_{ik}$ is the interaction term between treatment group i and time k .

$(\alpha M_{\text{baseline}})_{ijk}$ is baseline measurement-by-week interaction term for subject j in treatment group i at time k , and

error_{ijk} is the error term for subject j in treatment group i at time k .

An unstructured matrix for the within-subject error variance-covariance will be used. The denominator degrees of freedom will be calculated according to the Kenward-Roger method.

In case of non-convergence of the preferred model or memory space issues, the following back-up models are defined:

- The first backup model is the same as the preferred model, but the Kenward-Roger method will be replaced by Satterthwaite approximation.
- The second backup model is the same as the preferred model but without the term for baseline measurement-by-week interaction.

The second back-up model will only be provided if the first back-up model does not converge or has memory issues.

If the models do not converge, then the spatial power covariance matrix will be used instead.

The model will provide least-squares mean estimates, standard errors, and 2-sided 95% confidence intervals for mean change at all time points within and between treatments.

Appropriate diagnostics will be performed to check model assumptions.

Assessment of Treatment-by-Baseline Interaction:

Treatment-by-baseline interaction will be assessed for the analyses of the primary efficacy endpoint. In the repeated measures model (7.1.2.1), the interaction will be tested by including the additional terms for the treatment-by-baseline interaction.

The test for interaction will be performed at the 0.10 level of significance. If the treatment-by-baseline interaction is not significant, the original model (7.1.2.1) will be used. Otherwise, the interaction will be assessed as qualitative or quantitative.

If the regression lines do not cross, or the crossing is judged not severe (i.e., the crossing occurs near the boundary or beyond the range of baseline values), then the interaction will be considered quantitative and this does not compromise the validity of the treatment comparisons. In this case, the treatment comparisons will be made using the model without the treatment-by-baseline interaction term.

Otherwise, the interaction will be considered qualitative and treatment comparisons will not be presented as a result of the complete model. In this case, the impact of the baseline value on treatment effect will be investigated by summarizing the data in subsets defined by baseline categories.

Subgroup Analyses and Assessment of Treatment-by-Subgroup Interaction:

Treatment effects for the primary efficacy endpoint will be assessed for subgroups, in the ST analysis, based on age group, female age group, gender, race, region, baseline HbA1c categories, and baseline eGFR categories, as defined in Table 7.3.2A and Table 7.3.2B. The analyses will be based on model 7.1.2.1 with additional covariates of subgroups, treatment-by-subgroup, time-by-subgroup, and treatment-by-time-by-subgroup. Tests of the treatment-by-subgroup interaction will be assessed using contrasts of the treatment effect by subgroups at Week 52. The model to assess the treatment-by-baseline HbA1c interaction will include baseline HbA1c as a continuous variable. Adjusted mean change from baseline and its difference from the control group will be given for each subgroup at Week 52.

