8.4.2.1 Primary Efficacy Analysis

The primary efficacy analysis of HbA1c at Week 52 will be performed using a longitudinal repeated measures model with terms for treatment group, baseline value, time, the interaction of treatment and time, and the interaction of baseline value and time in the model, including observations prior to rescue. Point estimates and 95% confidence intervals will be calculated for the adjusted mean changes within each treatment group, as well as for the differences in adjusted mean changes between treatment groups.

Sensitivity analyses for HbA1c will include additional repeated measures analyses and analysis of covariance (ANCOVA) analyses. The repeated measures analyses will include two separate analyses, including values after rescue, and including and excluding a time-dependent covariate for rescue. Two separate ANCOVA analyses of the change from baseline at Week 52 will be performed, with terms for treatment group and baseline value in the model. One analysis will be based on measurements at Week 52 (if prior to rescue, if applicable) or the last post-baseline measurement prior to Week 52 and prior to rescue (if applicable), if no Week 52 assessment is available (eg, last observation carried forward [LOCF]). The second sensitivity analysis using ANCOVA will be based on all subjects completing the double-blind treatment period without requiring glycemic rescue therapy.

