8.4.7 Subgroup analysis

Subgroup analyses for age, gender, race, female age, region, and baseline HbA1c category for continuous endpoints will be analyzed as was done for the original analysis, but for the applicable subset of patients. Interaction tests will be performed for time to event and continuous endpoints using the original model with treatment interaction terms added.

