7.5 Efficacy

7.5.1 Overall Efficacy Summary

All efficacy analyses will be performed using the Randomized Subjects data set. In addition, at the ST analysis, the primary efficacy analysis will be performed using the Evaluable Subjects data set if > 10% of subjects in any treatment group have relevant protocol deviations.

Unless otherwise specified, all analyses will be done using values prior to rescue/intensification of treatment or treatment discontinuation (plus a tolerance window after last dose as detailed in Section 0). For the endpoint of the proportion of subjects achieving a therapeutic glycemic response at Week 52/Week 156, all available data will be used, but subjects rescued prior to Week 52/Week 156 will be treated as non-responders.

The comparator (glimepiride plus metformin) will be tested against saxagliptin, in co-administration with dapagliflozin plus metformin, for the primary efficacy endpoint at the alpha = 0.05 level (two-sided). The secondary efficacy endpoints will then be tested sequentially, each comparison tested at the alpha = 0.05 level (two-sided). The following testing hierarchy (shown in order of the step-wise testing sequence) for treatment comparisons will be used:

- Mean change from baseline in HbA1c at Week 52 (primary endpoint).
- Mean change from baseline in total body weight at Week 52.
- Percent of subjects achieving a therapeutic glycemic response, defined as HbA1c < 7.0%, at Week 52.
- Mean change from baseline in systolic blood pressure (SBP) at Week 52.
- Time to treatment intensification (addition of insulin or other glucose-lowering agent for rescue therapy or discontinuation for lack of glycemic control) during the 52-week double-blind treatment period.

If all the above five comparisons performed for the short-term analysis are statistically significant, the following two comparisons will be tested sequentially for the short-term plus long-term analysis:

- Time to treatment intensification (addition of insulin or other glucose-lowering agent for rescue therapy or discontinuation for lack of glycemic control) during the 156-week treatment period.
- Proportion of subjects achieving a therapeutic glycemic response, defined as HbA1c < 7.0%, at Week 156

Analyses of exploratory endpoints specifically designed for sub-studies (CGM and MRI-PDFF) will be performed using the subsets of the Randomized Subjects data set for the sub-studies.

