7.5.2 Primary Efficacy Analysis

The primary endpoint is the change in HbA1 from baseline at Week 52 visit. The primary analysis of the change in HbA1c from baseline at Week 52 visit will be based on a longitudinal repeated measures analysis using “direct likelihood”. The model will use subjects in the primary efficacy data set (i.e., randomized subjects data set) who have a baseline assessment and at least one post-baseline double-blind treatment period assessment. The SAS procedure PROC MIXED will be used. The preferred model will include the fixed categorical effects of treatment, week, and treatment-by-week interaction as well as the continuous fixed covariates of baseline measurement and baseline measurement-by-week interaction (see Model 7.1.2.1 in Section 7.1.2). An unstructured matrix for the within-subject error variance-covariance will be used. The denominator degrees of freedom will be calculated according to the Kenward-Roger method. A number of back-up models are defined in Section 7.1.2 in case of non-convergence of the preferred model or other issues. Data collected after the initiation of rescue medication will be excluded. Data collected outside the analysis window (defined in Section 8 of this SAP) after subjects discontinued double-blind study medication will also be excluded from the primary analysis. Point estimates and 95% confidence intervals for the mean change within each treatment group as well as the difference in mean change between the saxagliptin plus dapagliflozin versus glimepiride will be calculated.

Sensitivity Analyses

The following sensitivity analyses will be carried out for the primary end point for the ST data/at week 52:

- Primary analysis will be repeated using Evaluable Subjects data set.
- Primary analysis will be repeated using all available values regardless of rescue or treatment discontinuation
- An ANCOVA analysis using values prior to rescue or treatment discontinuation (LOCF will be used if the week 52 value is not available)
- Analyses to address missing values (described below in Section 7.5.4)
 - Analysis using multiple imputation return-to-baseline
 - Tipping point analysis

The following sensitivity analyses will be carried out for the ST+LT data/at Week 156 are: .

- Change from baseline in HbA1c at week 156, ANCOVA (LOCF) using the Randomized subject data set - completers not requiring glycemic rescue therapy, (defined as subjects who

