7.5.6 Summary of Primary Efficacy Endpoint within Subgroups

Treatment effects will be assessed for subgroups based on age group, female age group, gender, race, region, baseline HbA1c categories, and baseline eGFR categories as defined in Table 7.3.2A and Table 7.3.2B. The analyses will be based on model 7.1.2.1 with additional covariates of subgroups, treatment-by-subgroup, time-by-subgroup, and treatment-by-time-by-subgroup. The nominal p-value for subgroup-by-treatment interaction will be presented. The p-value for the test of treatment by age, female age, baseline HbA1c, and baseline eGFR interaction will include corresponding continuous subgroup variables in the model. Adjusted mean change from baseline and its difference from the control group will be given for each subgroup at week 52.

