10 CHANGES OF ANALYSIS FROM PROTOCOL

Changes from Protocol prior to short-term data base lock are summarized in the following table:

Changes	Reason for changes
Definition of Full Analysis Set was added.	To be consistent with other saxagliptin plus dapagliflozin studies.
Summary and analysis of SMBG data was updated.	To be consistent with other saxagliptin plus dapagliflozin studies.
Definition of Confirmed hypoglycemia was updated to consider all events with glucose values ≤ 70 mg/dL (3.9 mmol/L) as recorded in the hypoglycemia module of the CRF	To avoid error in summarizing data based on glucose values which were not collected using consistent methods.

Changes	Reason for changes
irrespective of the method using which glucose data were collected.	
MI sensitivity analyses for primary endpoint were added.	To be consistent with other saxagliptin plus dapagliflozin studies.

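### A 0.10-level interaction test plus an unquantified judgement can withhold the primary HbA1c comparison, in conflict with SAP 7.5.2 and with no rule for the testing hierarchy

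*SAP*

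**What the plan says.** SAP 7.1.2 adds treatment-by-baseline terms to the primary repeated measures model (Model 7.1.2.1) and tests them at 0.10. There are three outcomes:

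- Not significant: Model 7.1.2.1 is used.
- Significant, but the regression lines do not cross or the crossing is judged not severe: the interaction is called quantitative and the model without it is used. The only guidance on not severe is that "the crossing occurs near the boundary or beyond the range of baseline values".
- Significant and none of the above: "Otherwise, the interaction will be considered qualitative and treatment comparisons will not be presented as a result of the complete model". The data are then summarised in baseline categories, and no test is attached to those summaries.

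SAP 7.5.2 sets no such condition: "the difference in mean change between the saxagliptin plus dapagliflozin versus glimepiride will be calculated". It points to 7.1.2 for the model and for back-ups used on non-convergence or other problems, and does not mention the interaction step. Protocol 8.4.2.1 is equally plain: "The primary efficacy analysis of HbA1c at Week 52 will be performed using a longitudinal repeated measures model".

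SAP 7.5.1 opens the fixed sequence with this comparison. The two Week 156 tests follow only under this condition: "If all the above five comparisons performed for the short-term analysis are statistically significant".

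**The concern.** A statistician following 7.1.2 and one following 7.5.2 could disagree on whether the trial has a primary result at all. The choice between them turns on a judgement that has no numeric limit, no named judge and no requirement for blinding. It is made on lines fitted by treatment group, so after the sponsor is unblinded.

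If the comparison is withheld, 7.5.1 does not say whether the sequence stops, whether a subset analysis stands in, or whether body weight is tested next. The Week 156 tests hang on the same chain.

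The protocol foresees interaction testing in 8.4.7 ("Interaction tests will be performed for time to event and continuous endpoints using the original model with treatment interaction terms added") but no withholding step. SAP Section 10 ("Changes from Protocol prior to short-term data base lock are summarized in the following table") does not list one.

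What is at stake is losing a valid positive result, or having to argue after the fact about whether it counts.

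**Working it through.** **Inputs from the documents.** Difference 0.35, SD 1.1, two-sided alpha 0.05, 5% non-evaluable, 220 per arm, 90% power (SAP 5). Pre-test level 0.10 (SAP 7.1.2). Entry HbA1c 7.5 to 10.5, with at most 40% of subjects in 7.5 to 8.5 (Protocol 3.3.1).

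**The plan's own figure.** n per arm = 2 × (1.960 + 1.282)² × 1.1² / 0.35² = 207.6, so 208 evaluable. 208 / 0.95 = 218.9, so 219, against 220 stated. With 220 × 0.95 = 209 evaluable per arm, power is 90.2%. The plan's figure is reproduced.

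**Assumptions added.**
- Baseline: 40% uniform on 7.5–8.5 and 60% uniform on 8.5–10.5, so mean = 0.4 × 8.0 + 0.6 × 9.5 = 8.9.
- Residual SD 1.1; the treatment effect is linear in baseline and averages 0.35.
- A Week 52 ANCOVA stands in for the repeated measures model.
- A crossing counts as severe if it lies within the observed 25th–75th baseline percentiles (strict) or 10th–90th percentiles (wide).

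**Rule simulated.** Withhold if interaction p < 0.10 and the crossing is severe. Reported power is the chance that the main model is significant in favour of the combination and is not withheld. There were 40,000 trials per scenario with 209 per arm.

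| Effect slope per 1% of baseline | Withheld, strict to wide | Reported power, strict to wide |
|---|---|---|
| 0 | 0.8% to 3.3% | 90.2% to 88.0% |
| 0.1 | 2.3% to 7.7% | 89.4% to 84.6% |
| 0.2 | 8.2% to 22.7% | 85.6% to 71.9% |

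Without the rule, main-model power is 90.4% at slope 0 and 89.5% at slope 0.2.

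**Is the withholding warranted at slope 0.2?** The true lines cross at 8.9 − 0.35/0.2 = 7.15, below the 7.5 entry limit. The true difference is 0.35 + 0.2 × (7.5 − 8.9) = 0.07 at 7.5 and 0.35 + 0.2 × (10.5 − 8.9) = 0.67 at 10.5. No eligible subject has a reversed effect in this scenario, so each withholding is a false alarm.

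**Slope 0.3 is not used as evidence.** The crossing is then 8.9 − 0.35/0.3 = 7.73, inside the entry range, with 0.40 × 0.233, about 9%, of subjects below it. Part of the 20% to 47% withholding there is the rule doing its job.

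**Robustness.**
- With baseline uniform on 7.5–10.5 (20,000 trials), withholding is 0.9% to 3.7% at slope 0 and 7.4% to 24.8% at slope 0.2.
- A separate simulation (4,000 trials per setting) used the 40/60 mix and a truncated normal baseline (mean 8.5, SD 0.8). It trimmed 0% to 25% of the observed range at each end as near the boundary. With no interaction and an effect of 0.35, about 1% to 8% of trials were withheld and reported power was 83% to 90%. At an effect of 0.20, withholding was about 5% to 10%.

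**Type I error.** With no treatment effect, false superiority is 2.6% without the rule and 2.4% to 2.6% with it. Two-sided rejection in the separate simulation was 4.6% to 5.2% without the rule and 4.2% to 5.0% with it. The rule only removes results.

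**The case against.** **The two sections can be read as default and exception.** SAP 7.5.2 refers to 7.1.2, and 7.1.2 says the assessment applies to the primary endpoint. The term complete model is undefined and might mean the model with the added interaction terms, or one overall model as opposed to subsets. The ambiguity is real, though withholding is the natural reading. On any reading, no substitute primary test is named, so the gap remains.

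**The hierarchy has a cautious default.** A comparison that is not presented has not been shown significant, so the sequence would stop. That is sensible, but the SAP does not say it, and it would forfeit every later test.

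**The larger figures are assumption-driven.** This stands. The documents give no slope. The 22.7% and 71.9% need both slope 0.2 and the wide reading. The statement about false alarms holds only for a linear effect. SAP 7.1.2 does not say whether the added terms are pooled over visits or specific to Week 52, so trigger rates in the repeated measures model may differ from those of a single-visit ANCOVA.

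**The crossing criterion is described.** Also fair: what counts as not severe is explained in words. Only the limit is missing.

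**SAP 7.5.6 may not fit the identical interaction.** Its subgroup model carries additional time terms. It still addresses whether the effect depends on baseline HbA1c, and there "The nominal p-value for subgroup-by-treatment interaction will be presented", with no consequence for the primary test.

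**The change would come after unblinding.** SAP version 3 was prepared after short-term reporting had begun, and removing a rule that can only delete a positive result then looks like a relaxation. This is the most serious objection. It calls for a documented justification and disclosure, not for leaving the contradiction in place.

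**Conclusion.** The concern holds and should be fixed. The contradiction between SAP 7.1.2 and SAP 7.5.2, and the silence of 7.5.1, are matters of text and need no simulation.

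The practical size is small under the planning assumptions: 0.2 to 2.4 points of power (90.4% against 90.2% to 88.0%). It becomes material if the effect rises moderately with baseline HbA1c: at an assumed slope of 0.2 the loss is 3.9 points (89.5 − 85.6) to 17.6 points (89.5 − 71.9). These sizes rest on the assumed slopes, baseline mix and percentile cut-offs, and on the ANCOVA stand-in. The harm is an ambiguous or lost confirmatory result, not a false positive.

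**What to change.** - In SAP 7.1.2, delete the sentence that withholds the comparison.
- In 7.1.2, 7.5.1 and 7.5.2, state that the Week 52 estimate, confidence interval and p-value from Model 7.1.2.1, or from its convergence back-ups, are always reported and always drive the hierarchy.
- Keep the interaction test, fitted lines and baseline-category estimates as supportive description, in line with 7.5.6.
- Enter the change in Section 10, give the reason for making it after short-term unblinding, and disclose whether the interaction was significant and judged qualitative in the Week 52 analysis.

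The cost is wording in three sections, one Section 10 entry and the documented justification. No new data or analyses are needed, and the planned 90% power and 0.05 alpha are unchanged.
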